7.2 Handling of Missing Data and Outliers

7.2.1 Missing Data Analysis Methods

For the primary and exploratory endpoint analyses using CT/GC infection, any subject that does not have a known infection status through Visit 5 (eg, is deemed lost to follow-up) will be considered a failure. Likewise, any subject that uses prohibited antibiotics during the treatment period of the study (through Visit 5) regardless of CT/GC infection status will be considered a primary endpoint failure. Lastly, any patient who receives an invalid CT/GC test result at Visit 5 will be considered a failure. All other analyses will be conducted using data as observed in the study with no imputation.

For the EMA parallel primary endpoints and the FDA secondary endpoint analyses of separate CT and GC infections, any subject that does not have a known infection status through Visit 5 (eg, is deemed lost to follow-up or discontinued but was not lost to follow-up) will be assumed to have not had a CT/GC infection. Any subject that uses prohibited medications for CT or GC will be considered failures in those respective endpoints. Lastly, any patient who received an invalid CT/GC test result at Visit 5 will be considered a failure. All other analyses will be conducted using data as observed in the study with no imputation.

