Subjects will return for a follow-up visit 4 weeks after the intervention period or after their last dose of study medication. At this time, CT/GC NAAT (vaginal swab), pregnancy (uHCG) testing, gynecological exam, and eDiary review will be performed.

Figure 1 Schematic Flow of Study Design

Abbreviations: CT = *Chlamydia trachomatis*, GC = *Neisseria gonorrhoeae*, NAAT = nucleic acid amplification test

⁽¹⁾In the event a subject has CT or GC infection diagnosed at a local healthcare facility during the period between visits, the infection and treatment will be documented and every effort to obtain a medical record will be made.

Screening and Eligibility

Subjects who consent may be screened if they have a known case of CT or GC within 17 weeks of enrollment, or suspicion of current CT or GC infection (subsequently confirmed with NAAT test at Screening Visit). Subjects randomized within 35 days of initial screening do not need to be re-screened.

Intervention and Follow-up Period

The intervention period is defined as Visits 1 to 5. There will be one follow-up visit (Visit 6), 4 weeks after the last intervention visit or last dose of study product. These periods are outlined in the schedule of assessments (Table 2). The protocol-defined period of observation is 20 weeks. In the event a subject has CT or GC infection diagnosed at a local healthcare facility during the period between visits, the infection and treatment will be documented and every effort to obtain a medical record will be made. These subjects will be considered as failures.

Safety Follow-up After Protocol-defined Period of Observation

This period includes safety follow-up as required by Good Clinical Practice (GCP) and standard clinical study practice. Adverse events determined to be at least possibly related to the

investigational product continuing after the final study visit (Visit 6) will be followed until resolution or stable status as determined by the Investigator.

Study Conduct Strategies due to Coronavirus Disease -2019

Based on the US Food and Drug Administration (FDA) guidance, Coronavirus disease 2019 (COVID-19) strategies are planned for this study to ensure adherence to best practices for study conduct.

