4 STUDY ENDPOINTS

4.1 Primary Endpoint

- The primary efficacy endpoint is the proportion of subjects who are defined as study successes versus study failures among the intervention groups (EVO100 or placebo).
Estimand Framework
 - FDA Submission
 - Success is defined as subjects completing the trial to Visit 5 without any of the following: CT/GC infection, usage of prohibited antibiotics during the study, an invalid CT/GC test at Visit 5.
 - The mITT population will be used, and the Chi-Square test will be used to compare the failure rates in EVO100 and placebo.
 - EMA Submission
 - The parallel primary efficacy endpoints define success through Visit 5 as:
 - CT Infection Endpoint:
 - The proportion of subjects without a CT infection, CT prohibited antibiotics, or invalid Visit 5 CT test.
 - GC Infection Endpoint
 - The proportion of subjects without a GC infection, GC prohibited antibiotics, or invalid Visit 5 GC test.
 - The mITT population will be used and the Chi-Square test will be used to compare the failure rates in EVO100 and placebo.

Note: These two parallel primary endpoints enable efficacy to be assessed separately for CT and GC. In this way, if the study is successful for either CT or GC but not for both, an indication for prevention of just one of the two pathogens could still be granted. Both primary endpoints will be tested at the 0.05 significance level (with no adjustments for multiplicity of statistical testing).

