8.4.4 Concomitant Medications

Concomitant medications will be assessed and includes any medication that would be taken during the study including all over the counter medications, vitamins, and nutritional supplements.

Medications used in this study will be coded by using latest version of World Health Organization (WHO) drug dictionaries.

Concomitant medications will be summarized descriptively using frequency tables by anatomical therapeutic chemical (ATC) class level 2 and preferred name by treatment group and overall based on ITT population. Concomitant medications will be listed. Additionally, a listing of subjects taking prohibited medications for intercurrent infections other than CT or GC will be provided.

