In addition, a sensitivity analysis will be provided for the primary endpoint. For the sensitivity analysis, the proportion of subjects who are defined as study successes will be irrespective of the use of prohibited antibiotics. Success will be defined as no CT/GC infection through Visit 5 (i.e., at least through study day 105). The statistical analysis described for the primary endpoint will be used for the secondary and sensitivity analyses.

A listing will be provided for CT/GC NAAT sample result.

EMA Analysis

For the parallel primary analyses, the proportion of subjects who are defined study successes will be compared between intervention groups (EVO100 or placebo) using a Chi-Square test. The primary efficacy will be completed using the subjects deemed analyzable* from the mITT population.

*All subjects in the mITT population are deemed analyzable for the purpose of the primary endpoint analysis. Those subjects who are in ITT but not in mITT will be excluded from said

analysis. The primary analysis will be performed using all subjects in the mITT population.

For the CT infection endpoint, success will be defined as having no CT infection, taking no CT prohibited medications, and no invalid CT test at Visit 5. For the GC infection endpoint, successes will be defined as having no GC infection, taking no GC prohibited medications, and no invalid GC test at Visit 5.

The primary statistical hypothesis being tested is that there is no difference in the proportion of subjects deemed study success in the EVO100 intervention group versus placebo. In statistical terms:

$$H0: pEVO100 = pplacebo, HA: pEVO100 \neq pplacebo$$

where, pEVO100 and pplacebo denote the proportion of subjects deemed a study success while on EVO100 or placebo, respectively. Denominators for percentages are number of subjects in the mITT population in each intervention group. To test superiority over placebo, the percentage of study successes will be compared against placebo based using Chi-Square test. The estimated difference in proportions, 95% confidence interval, and p-value will be presented. A two-sided 5% type I error rate ($\alpha=0.05$) will be used. The Fisher's Exact test will be conducted in place of the Chi-Square test if necessary due to issues with the expected cell counts.

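### The separate CT and GC endpoints count a pathogen's prohibited antibiotics as failure with no stated exemption for treating the other study infection, so an effect on one pathogen can appear as prevention of the other

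*SAP*

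**What the plan says.** SAP 4.1 (EMA Submission) defines success on the CT endpoint as "The proportion of subjects without a CT infection, CT prohibited antibiotics, or invalid Visit 5 CT test" and on the GC endpoint as "The proportion of subjects without a GC infection, GC prohibited antibiotics, or invalid Visit 5 GC test". It introduces both as running through Visit 5. SAP 8.6.2 (EMA Analysis) repeats the rule. For CT, for example, "success will be defined as having no CT infection, taking no CT prohibited medications, and no invalid CT test at Visit 5". SAP 7.2.1 puts it as a failure rule: "Any subject that uses prohibited medications for CT or GC will be considered failures in those respective endpoints". That sentence gives no time window. SAP 4.2 and 8.6.2 carry the same definitions into the FDA CT-only and GC-only secondary analyses.

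The purpose is given in the note to SAP 4.1: "These two parallel primary endpoints enable efficacy to be assessed separately for CT and GC". A claim for one pathogen alone is foreseen, and each endpoint is tested at 0.05 without multiplicity adjustment.

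The only text that sorts prohibited drugs by the reason for use is in SAP 8.4.4, where "a listing of subjects taking prohibited medications for intercurrent infections other than CT or GC will be provided". It changes no endpoint. The sensitivity analysis that ignores prohibited antibiotics (SAP 8.6.2) is specified for the FDA composite. None is stated for the separate endpoints.

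**The concern.** In the FDA composite the antibiotic rule does little harm of this kind, because a woman with CT has already failed. In a single-pathogen endpoint it can add failures that have nothing to do with that pathogen. A woman who has only CT and whose treatment is on the GC list becomes a GC failure without GC. If EVO100 lowers CT, fewer women in that arm receive such treatment, so the added GC failures differ between arms. The same can happen from GC to CT.

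At stake is the single-pathogen claim itself. A trial with an effect on one pathogen could reach significance on both separate endpoints. Leaving the point open also lets two programmers score the same woman differently on a primary endpoint.

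**Working it through.** **1. The plan's own figure.** SAP section 5 assumes composite failure of 37.5% versus 30.5%, two-sided 0.05, and 821 analyzable women per arm. The check uses a chi-square (pooled z) test:

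power = 1 − Φ[(1.96·SE0 − d)/SE1] + Φ[(−1.96·SE0 − d)/SE1],

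with SE0 = √[2p̄(1−p̄)/n] and SE1 = √[p0(1−p0)/n + p1(1−p1)/n]. Here d = 0.070, SE0 = 0.02338 and SE1 = 0.02332, so power is 85.0%, as stated. The SAP gives no power for the separate endpoints.

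**2. Model for the GC endpoint.** Let g be the GC rate (equal in both arms, so no GC effect), c the CT rate in an arm, and f the share of CT-infected women who receive a GC-listed antibiotic within the scoring window. With infections independent and no other source of failure,

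GC-endpoint failure = g + (1 − g)·f·c.

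**3. Assumed inputs.** The documents give none of g, c or f. The main case takes g = 3% and CT 20% on placebo versus 13% on EVO100, which puts the whole planned 7-point difference on CT.

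**4. One case in full (f = 0.25).** Placebo: 0.03 + 0.97 × 0.25 × 0.20 = 0.0785. EVO100: 0.03 + 0.97 × 0.25 × 0.13 = 0.0615. So d = 0.0170 and SE0 = SE1 = 0.01259. Then (1.96 × 0.01259 − 0.0170)/0.01259 = 0.61, and 1 − Φ(0.61) = 0.27.

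**5. Range.** The last column repeats the calculation with CT 15% versus 10%.

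| f | GC-endpoint failure, placebo vs EVO100 (CT 20 vs 13) | Chance of p<0.05, no GC effect | Same, CT 15 vs 10 |
|---|---|---|---|
| 0 | 3.0% vs 3.0% | 5% | 5% |
| 0.10 | 4.9% vs 4.3% | 10% | 8% |
| 0.25 | 7.9% vs 6.2% | 27% | 18% |
| 0.50 | 12.7% vs 9.3% | 59% | 40% |

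When f is above zero, nearly all of these rejections favour EVO100 in the main case.

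**6. Upper end.** Post-enrollment tests fall at Visits 2 to 5, and swabs go to a central laboratory (SAP 8.7.2). An infection first found at Visit 5 would therefore be treated after the window. If detection is spread evenly over the four visits, about a quarter of cases cannot leak, and f stays at or below about 0.75 even with complete overlap. At f = 0.75 the main case gives 82%, and CT 15% versus 10% gives 62%.

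**7. Reverse direction.** With GC 6% versus 3% and CT 15% in both arms, CT-endpoint failure at f = 0.5 is 0.15 + 0.85 × 0.5 × 0.06 = 17.6% versus 0.15 + 0.85 × 0.5 × 0.03 = 16.3%. The chance of a false CT result is 11%.

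**8. After an exemption.** With f = 0 the rate returns to 5%, apart from the exit rule. The protocol synopsis (Treatment Duration) ends participation at a positive test, and SAP 7.2.1 counts unknown status on the separate endpoints as not infected. With constant hazards h = −ln(1 − rate), observed GC = [h_g/(h_g + h_c)]·[1 − exp(−(h_g + h_c))]. For g = 3% this gives 2.69% on placebo versus 2.80% on EVO100. For g = 5% it gives 4.49% versus 4.67%, with 1.6% of trials falsely favouring EVO100 against a nominal 2.5%. The residual bias is small and against EVO100.

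**The case against.** The strongest reply is that the harm needs two things the documents do not show: overlapping lists, and treatment of a study infection counting as prohibited use within the window. Only the protocol synopsis is available, so a definition or an exemption may be in the full protocol. The SAP 7.2.1 sentence could also be read by indication, meaning drugs taken for that infection, which would remove the leak. This stands as a limit on size. It does not settle the scoring, because the wording in SAP 4.1 reads more naturally as a drug list.

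A reader might infer that every positive woman's treatment is recorded and scored. The documents do not say so. SAP 3.1 says that "the infection and treatment will be documented and every effort to obtain a medical record will be made", but only for infections diagnosed at a local facility between visits. Standard-of-care treatment is described only for women positive at screening. Nor does SAP 8.4.4 show that a drug is prohibited whatever it was given for. Its listing is confined to infections other than CT or GC, which fits equally well with treatment of study infections not counting.

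Counting an antibiotic that could mask GC as a GC failure is also a defensible composite strategy. That supports keeping the present rule as a sensitivity analysis. It is a weak basis for a single-pathogen claim when the other pathogen drives the antibiotic use.

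Finally, SAP 4.3 plans failure components for the FDA and EMA endpoints, and SAP 8.6.3 tabulates infections and antibiotics separately. A GC difference made up of antibiotic failures would be partly visible there, but the primary test would not change.

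**Conclusion.** The point holds as a conditional one. The rule appears in three places without an exemption, and no sensitivity analysis that ignores antibiotics is stated for the separate endpoints. As written, an effect on one pathogen can carry into the other's endpoint, against the purpose in SAP 4.1.

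The size depends on assumed pathogen rates, on f, and on independent infections. In the main case a 5% error rate becomes 10% at f = 0.10 and 59% at f = 0.50. It is lower with a smaller CT effect and in the GC-to-CT example. If the lists do not overlap it stays at 5%.

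A reader might take full leakage (f = 1, 94% in the main case) as the expected result, or treat this as a proven error that invalidates the EMA analysis. The documents support neither. Treatment after Visit 5 falls outside the window, the exit rule may remove more, and the lists are not available. This is a gap to close before unblinding. The stated sample size is correct and unaffected.

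**What to change.** In SAP 4.1, 7.2.1 and 8.6.2, for the CT-only and GC-only endpoints (EMA primaries and FDA secondaries):

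- State that an antibiotic given after and because of a documented infection with the other pathogen is not by itself a failure. Score the woman on her available NAAT results for this pathogen, with the existing unknown-status rule if none follow.
- State that the antibiotic rule runs through Visit 5. Define or cite the CT and GC lists.
- Leave antibiotics taken for any other reason under the present rule.
- Keep the present all-antibiotics rule as a sensitivity analysis. Add an infection-only sensitivity analysis for each separate endpoint, as already planned for the FDA composite.

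The work is SAP wording and one derived flag from the medication's indication and date. The statistical cost is fewer failures on each separate endpoint, possibly many fewer if the lists overlap: in the main case at f = 0.5, placebo GC failure falls from 12.7% to 3.0% (821 × 0.127 = 104 women to 821 × 0.03 = 25). Women who leave at a positive test for one pathogen would be counted as negative for the other, a small bias against EVO100.

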7.2.2 Handling of Missing or Incomplete Dates

Imputation rules for missing or partial AE start date are defined below:

If only Day of AE start date is missing:

If the AE start year and month are the same as that for the first dose date, then:

- If the full (or partial) AE end date is NOT before the first dose date or AE end date is missing, then impute the AE start day as the day of first dose date; otherwise, impute the AE start day as 1.
- If the full (or partial) AE end date IS before the first dose date, the AE will be classified as a pre-treatment AE.

Compare the imputed AE start date with TE period to determine whether the AE is pre-treatment AE, TEAE or post-treatment AE.

If Day and Month of AE start date are missing:

If AE start year = first dose year, then:

- If the full (or partial) AE end date is NOT before the first dose date or AE end date is missing, then impute the AE start Month and Day as the Month and Day of first dose

date; otherwise, impute the AE start Month as January and the Day as 1.

- If the full (or partial) AE end date IS before the first dose date, the AE will be classified as a pre-treatment AE.

Compare the imputed AE start date with TE period to determine whether the AE is pre-treatment AE, TEAE or post-treatment AE.

If Year of AE start date is missing:

If the year of AE start is missing or AE start date is completely missing, then query site with no imputation. Also compare the full (or partial) AE end date to the first dose date. If the AE end date is before the first dose date, then the AE should be considered as a pre-treatment AE. Otherwise, the AE will be considered as TEAE.

Imputation rules for missing or partial medication start/stop dates are defined below:

Missing or partial medication start date:

- If only DAY is missing, use the first day of the month.
- If DAY and Month are both missing, use the first day of the year.
- If DAY, Month and Year are all missing, use a date before the first dose date.

Missing or partial medication stop date:

- If only DAY is missing, use the last day of the month.
- If DAY and Month are both missing, use the last day of the year.
- If DAY, Month and year are all missing, assign ‘continuing’ status to stop date.

8 STATISTICAL METHODS

8.1 General Statistical Conventions

All statistical procedures will be completed using SAS version 9.4 or higher.

Unless otherwise stated, all statistical testing will be two-sided and will be performed using a significance (alpha) level of 0.05. Two-sided 95% confidence intervals (CIs) will be provided when relevant.

For continuous variables, descriptive statistics will include the number of non-missing values (n), mean, standard deviation, median, minimum, and maximum. For categorical variables, descriptive statistics will include counts and percentages per category. All summaries will be presented by treatment group and overall, unless otherwise specified.

Baseline values for all parameters will be the most recent value prior to administration of study product or speculum examination.

All subject data will be presented in individual subject data listings. Unless otherwise stated, unscheduled visit results will be included in date/time chronological order, within subject listings only. All listings will be sorted by investigational site, subject number, and visit. The treatment group (EVO100, Placebo) as well as subject's age and sex (if available) will be stated on each listing. With respect to study tables, the mITT population will be used for efficacy analyses; safety population will be used for safety analyses.

8.2 Subject Disposition

Subject disposition information will be summarized by treatment group and overall. The number and percent of subjects who are randomized, who complete the study treatment, who complete the study and who withdraw early from the treatment and study will be presented.

The primary reason for early withdrawal from treatment and/or the study will also be tabulated.

The number of subjects randomized will be used as the denominator for the percentage calculation.

The number and percent of subjects in each analysis set will also be tabulated.

Subject disposition including primary reason to indicate why subject was not randomized will be listed.

The number of subjects excluded from ITT, mITT, Safety analyses sets and reasons for exclusion will be summarized by treatment group and overall. Listings will also be provided for subjects excluded from the analysis set with reasons for exclusion.

8.3 Protocol Deviations

All key protocol deviations identified will be summarized by treatment group and overall based on ITT population.

A listing will include the inclusion/exclusion criteria violated at screening and enrollment visits as well as other key protocol deviations.

To explore potential changes in study conduct due to COVID-19 (e.g., flexibility regarding

Screening window, visit time-frames, and follow-up were allowed in order to capture more touchpoints within a patient's timeline during the study), an additional analysis will be performed to recognize and indicate the impact of participation of subjects by COVID-19. The impact of COVID-19 will be summarized by treatment group and overall by visit for all subjects in ITT population. This table will present the subjects affected by COVID-19 in all aspects (e.g., missed visit and/or assessment due to COVID-19, remote visit due to COVID-19, modified assessment due COVID-19). In addition, key protocol deviations related to COVID-19 will also be summarized using ITT population.

A by-subject listing will also be provided for all subjects that have their participation impacted by COVID-19.

8.4 Demographics and Baseline Characteristics

8.4.1 Demographics

Demographic variables include age, race, ethnicity, height, weight, BMI and will be summarized and listed using ITT population. Continuous measures will be summarized treatment group and overall using descriptive statistics (n, mean median, standard deviation, minimum, and maximum). Categorical variables will be summarized by treatment group and overall using frequency counts and percentages. All demographic information will be presented in a subject-level listing.

8.4.2 Baseline and Disease Characteristics

The baseline characteristics includes CT/GC infection history, gynecological exam details, current contraceptive methods used, vaginal pH, CT/GC NAAT sample result, risk factors and vital signs. Categorical variables summarized using frequency counts and continuous variables will be summarised by descriptive statistics using ITT population. Baseline characteristics will be listed.

8.4.3 Medical History

A summary of medical/surgical/gynecologic/sexual health history will be presented by system organ class and preferred term (PT) using Medical Dictionary for Regulatory Affairs® (MedDRA) version 23 or higher based on ITT population. Medical history will be listed.

